6.4.4. Dose Modification, Dose Delays, and Retreatment Criteria for Platinum Chemotherapy

Dose modifications must be based on the maximum toxicity experienced during a cycle. The investigator may attribute each toxicity event to platinum chemotherapy alone or to the combination of study drugs. Dose modification of the platinum chemotherapy agent and not the other agent(s) is appropriate if, in the opinion of the investigator, the toxicity is clearly related to platinum chemotherapy. If the toxicity is related to a combination of agents, all relevant agents should be reduced (if applicable), interrupted or discontinued according to the recommended dose modifications for that agent. See Section [6.2.2](#) for the dose modification, dose delay, and retreatment instruction for erdafitinib. See Section [6.3.1](#) and [6.3.2](#) for instructions regarding the retreatment and dose delay of cetrelimab, respectively.

If a subject experiences several toxicities and there are conflicting recommendations, the most conservative dose adjustment recommended should be followed (dose reduction appropriate to the most severe toxicity). Subjects can have a maximum of 2 dose modifications (if applicable) of platinum chemotherapy throughout the course of the study for toxicities. Subjects who require a 3rd dose modification to any particular component will have that agent discontinued.

Recommended dose modifications for platinum chemotherapy for hematologic and non-hematologic toxicity are described in [Appendix 2 Table 5](#) and [Appendix 2 Table 6](#), respectively. [Appendix 2 Table 5](#) and [Appendix 2 Table 6](#) serve as a guide and do not replace investigator judgment and applicable local label recommendations if more stringent.

Appendix 2 Table 5: Recommended Dose Modifications for Platinum Chemotherapy: Hematological Toxicity

		Cisplatin/Carboplatin	
		Dose modification (DM)	
Platelets ($\times 10^3$ cells/microliter)	ANC ($\times 10^3$ cells/mm 3)	DM 0	DM 0
≥ 50 AND	≥ 0.5	DM 0	DM 0
≥ 50 AND	<0.5	DM -1	DM -1
<50 without bleeding AND	ANY	DM -1	DM -1
<50 with Grade ≥ 2 bleeding AND	ANY	DM -2	DM -2
ANY AND	$<1.0 +$ fever $\geq 38.5^{\circ}\text{C}$ (101°F)	DM -1	DM -1

Appendix 2 Table 6: Recommended Dose Modifications for Platinum Chemotherapy: Non-Hematological Toxicity

Event	CTC Grade	Cisplatin	Carboplatin
		Dose modification (DM)	
Nausea or vomiting	Grade 3 or 4	DM 0	DM 0
Diarrhea	Grade 3 or 4	DM -1	DM 0
Mucositis	Grade 3 or 4	DM 0	DM 0
Neurotoxicity	Grade 2	DM -2	DM 0
	Grade 3 or 4	Discontinue	DM -1
Transaminase elevation	Grade 3	DM -1	DM -1
	Grade 4	Discontinue	Discontinue
Other non-hematological toxicity	Grade 3 or 4	DM -1	DM -1

Appendix 2 Table 7 : Dose Modifications for Cisplatin and Carboplatin

Category	Cisplatin		Carboplatin	
Starting dose	50 mg/m ²	60 mg/m ²	AUC 4 mg/mL/min (maximum dose 600 mg)	AUC 5 mg/mL/min (maximum dose 750 mg)
1st dose modification	Stop cisplatin but continue erdafitinib+ cetrelimab	50 mg/m ²	Stop carboplatin but continue erdafitinib+ cetrelimab	AUC 4.5 mg/mL/min (maximum dose 675 mg)
2nd dose modification	N/A	Stop cisplatin but continue erdafitinib+ cetrelimab	N/A	Stop carboplatin but continue erdafitinib+ cetrelimab

Creatinine clearance (CrCl)

CrCl will be based on the original weight-based Cockcroft and Gault formula ([Attachment 8](#)). The subject's CrCl at Screening must be ≥ 30 mL/min to receive carboplatin and ≥ 60 mL/min to receive cisplatin prior to each cycle of platinum chemotherapy. Cisplatin may be delayed for up to 21 days (1 cycle) to allow the subject time to recover from the toxicity. If a subject's CrCl value has not returned to ≥ 30 mL/min within 42 days (2 cycles) after the previous dose, cisplatin must be discontinued.

In general, study drug(s) should be held for AEs \geq Grade 3 that are not attributable to erdafitinib, cetrelimab, platinum chemotherapy, or the disease under study. If the event resolves to Grade 1 or baseline within 4 weeks, platinum chemotherapy and erdafitinib may be reintroduced at one dose level lower. If the same toxicity does not recur or worsen within 4 weeks after re-starting therapy, then cetrelimab may be reintroduced at the same dose. Following re-introduction of study drugs, if the same AE recurs at \geq Grade 3 or there is a second incidence of a \geq Grade 3 event that is not attributable to erdafitinib, cetrelimab, platinum chemotherapy, or the disease under study, study drugs should be permanently discontinued.

For toxicity associated with platinum chemotherapy, the AE must resolve to Grade ≤ 1 or baseline prior to starting subsequent cycle. For individual subjects requiring a dose modification, treatment

for each new cycle may be delayed if the scheduled off-drug periods are not adequate to allow for recovery to Grade ≤ 1 or the baseline status of the subject.

If a subject permanently discontinues 1 of the study drugs, the subject may continue to receive the other study drug(s) if investigator believes that the subject derives clinical benefit upon consultation with the sponsor's responsible medical monitor. Communication with the sponsor's responsible medical monitor including the final decision must be documented and retained in the sponsor's trial master file and in the investigator's study files.

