Combining platinum (cisplatin or carboplatin) chemotherapy with targeted therapy and checkpoint inhibition may provide benefit to patients given the high response rate to chemotherapy in first line treatment, regardless of FGFR status. The addition of targeted therapy may deepen and lengthen that response.

Rationale for treatment in 1L mUC (Phase 2)

[figure not shown]
The management of metastatic urothelial cancer is driven by the global status of the patient including factors like ECOG PS Grade (0-1 versus 2), renal function (creatinine clearance [CrCl] $\geq 60\text{ml/min}/1.73\text{ m}^2$ versus CrCl $< 60\text{ ml/min}/1.73\text{ m}^2$) and presence of comorbidities (eg, hearing loss, cardiac dysfunction). Renal function for cisplatin-eligible patients is typically defined as CrCl $\geq 60\text{mL/min}/1.73\text{ m}^2$ versus cisplatin-ineligible CrCl $< 60\text{ ml/min}/1.73\text{ m}^2$ ([Dogliotti 2007](#)). Additionally, Grade 2 or higher hearing loss, ECOG PS of 2, or Grade 2 or higher peripheral neuropathy would also typically deem a patient ineligible for cisplatin ([Galsky 2011](#)). The global standard of care for both cis-eligible and cis-ineligible groups is combination chemotherapy. The standard of care for cisplatin-ineligible patients, includes combination chemotherapy of carboplatin and gemcitabine which has demonstrated an ORR of 39% for patients that have either ECOG 2 or CrCl $< 60\text{ ml/min}/1.73\text{ m}^2$, 26% for patients with both factors and 20% when adding the risk factor of visceral metastasis. Median PFS for cisplatin-ineligible patients is approximately 3 months ([Dogliotti 2007](#)). Significant hematologic toxicity is observed with both gemcitabine/cisplatin and gemcitabine/carboplatin chemotherapy regimens; Grade 3-4 neutropenia occurs in 34-45% of patients ([Dogliotti 2007](#)). Additionally, the risk of nephrotoxicity makes these therapies undesirable in up to half of patients with mUC who have concurrent renal insufficiency ([Rosenberg 2005](#)).

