		≥28 days prior to C1D1	Within 28 days prior to C1D1	Day 1 ^e	Day 8 (±2)	Day 15 (±2)	Day 1 (±2)	Day 8 (±2)	Day 15 (±2)	Day 1 (±2)	Day 1 (±2)	Day 8 (±2)	Day 15 (±2)	Day 1 (±2)	Within 30 Days (+7) of last dose	Every 12 weeks
Chemistry	May be obtained up to 2 days prior to each cetrelimab dose; for exact assessments, see Section 9.6.2.		X	X	X	X	X	X	X	X	X			X	X	
Creatinine clearance calculation	May be obtained up to 2 days prior to each cetrelimab dose; for exact assessments, see Section 9.6.2. CrCl is calculated by the Cockcroft-Gault formula (Attachment 8).		X	X	X	X	X	X	X	X	X					
PO ₄	May be obtained up to 2 days prior to each cetrelimab dose; for exact assessments, see Section 9.6.2.		X	X	X	X	X	X	X	X	X			X	X	
PTH	May be obtained up to 2 days prior to each cetrelimab dose; for exact assessments, see Section 9.6.2. After C6D1 PTH to be done every 3 rd cycle. Results not required before dosing.		X				X	X		X	X			X	X	

Assessments/ Procedure	Notes	Molecular Eligibility Screening Period	Full-Study Screening Period	Treatment Cycle 1 ^g			Treatment Cycle 2 ^g			Treatment Cycle 3 ^g	Treatment Cycle 4 ^g			All Other Cycles ^g	End-of- Treatment ^{a, g}	Follow- up Period ^{a, g}
		≥28 days prior to C1D1	Within 28 days prior to C1D1	Day 1 ^e	Day 8 (±2)	Day 15 (±2)	Day 1 (±2)	Day 8 (±2)	Day 15 (±2)	Day 1 (±2)	Day 1 (±2)	Day 8 (±2)	Day 15 (±2)	Day 1 (±2)	Within 30 Days (+7) of last dose	Every 12 weeks
TSH, T3, FT4	May be obtained up to 2 days prior to each cetrelimab dose; for exact assessments, see Section 9.6.2. T3 at Screening then only as clinically indicated.		X	Day 1 of every other cycle starting at C2D1												
Serology	See Section 9.6.2. Results obtained within 60 days of C1D1 are acceptable.		X													
Pregnancy test (pre-dose)	For women of childbearing potential, serum at Screening (β -hCG) - obtain \leq 7 days of C1D1. Serum or urine thereafter. See Section 9.6.4.		X				X			X	X			X	X	X ^c

Assessments/ Procedure	Notes	Molecular Eligibility Screening Period	Full-Study Screening Period	Treatment Cycle 1 ^g			Treatment Cycle 2 ^g			Treatment Cycle 3 ^g	Treatment Cycle 4 ^g			All Other Cycles ^g	End-of- Treatment ^{a, g}	Follow- up Period ^{a, g}
		≥28 days prior to C1D1	Within 28 days prior to C1D1	Day 1 ^e	Day 8 (±2)	Day 15 (±2)	Day 1 (±2)	Day 8 (±2)	Day 15 (±2)	Day 1 (±2)	Day 1 (±2)	Day 8 (±2)	Day 15 (±2)	Day 1 (±2)	Within 30 Days (+7) of last dose	Every 12 weeks
Efficacy Assessments																

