4.1. Inclusion Criteria

Each potential subject must satisfy all of the following criteria to be enrolled in the study:

1. ≥ 18 years of age.
2.
 - Criterion modified per Amendment 2
 - 2.1 Histologic demonstration of transitional cell carcinoma of the urothelium. Variant urothelial carcinoma histologies such as glandular or squamous differentiation, or evolution to more aggressive phenotypes such as sarcomatoid or micropapillary change are acceptable.
 - 3.
 - Criterion modified per Amendment 2
 - 3.1 Metastatic or locally advanced urothelial cancer (Stage IV disease per AJCC Staging Guidelines)
 - 4.
 - Criterion modified per Amendment 2
 - 4.1 Criterion modified per Amendment 3
 - 4.2 Phase 1b erdafitinib + cetrelimab cohort and Phase 2: Meet appropriate molecular eligibility criteria. Tumors must have at least one gene fusion or gene mutation as defined in [Table 4](#).

Exception for Phase 1b erdafitinib + cetrelimab + platinum chemotherapy cohort: up to 3 subjects in each erdafitinib + cetrelimab + chemotherapy cohort at each dose level will be wild-type. Wild-type is defined as subjects without FGFR gene alteration and subjects with FGFR gene alterations other than the select FGFR alterations

described in [Table 4](#). All other subjects must have at least one select FGFR alteration as defined in [Table 4](#).

5. Criterion modified per Amendment 2

5.1 Must have measurable disease by radiological imaging according to the Response Evaluation Criteria in Solid Tumors (RECIST, version 1.1) at baseline.

6. Criterion modified per Amendment 2

6.1 Criterion modified per Amendment 3

6.2 Prior systemic therapy for metastatic urothelial cancer:

Phase 1b erdafitinib + cetrelimab cohort:

- Any number of lines of prior therapy

Renal function for subjects must have a creatinine clearance (CrCl) ≥ 30 mL/min as calculated by Cockcroft-Gault ([Attachment 8](#))

Phase 1b erdafitinib + cetrelimab + platinum chemotherapy cohort:

- No prior systemic therapy for metastatic disease. **Note:** Subjects who received neoadjuvant or adjuvant chemotherapy and showed disease progression, within 12 months of the last dose are considered to have received systemic chemotherapy in the metastatic setting
- Renal function for subjects must have a creatinine clearance (CrCl) ≥ 30 mL/min to receive carboplatin and ≥ 60 mL/min to receive cisplatin as calculated by Cockcroft-Gault ([Attachment 8](#))

Phase 2:

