6.4.5. Guidance for Specific Platinum Chemotherapy Toxicities

Cisplatin

The toxicity profile for cisplatin is described in the full prescribing information and labeling in the respective current US prescribing information, EU SmPC, or equivalent document for the specific region/country.

For subjects in DL2C, DL2C1 and DL2C2, cisplatin may produce cumulative nephrotoxicity which is potentiated by aminoglycoside antibiotics. Serum creatinine, blood urea nitrogen (BUN), creatinine clearance, magnesium, sodium, potassium, and calcium levels should be measured prior to initiating therapy and prior to each dose of cisplatin. Adequate renal function must be documented prior to receiving the next dose of cisplatin.

Audiometry will be performed for cis-ineligible ONLY if hearing loss is the single reason for cis-ineligibility. Audiometry will be performed as clinically indicated as ototoxicity is cumulative. Hearing loss during the study should be reported as an AE and graded according to CTCAE version 5.0.

Carboplatin

The toxicity profile for carboplatin is described in the full prescribing information and labeling in the respective current US prescribing information, EU SmPC, or equivalent document for the specific region/country.

For subjects in DL2D and DL2D1, bone marrow suppression (leukopenia, neutropenia, and thrombocytopenia) is dose-dependent and is also a DLT. Peripheral blood counts should be monitored frequently and, when appropriate, until recovery is achieved. Carboplatin can induce emesis, which can be more severe in patients previously receiving emetogenic therapy.

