4.1. Inclusion Criteria

Each potential subject must satisfy all of the following criteria to be enrolled in the study:

1. ≥ 18 years of age.
2. Criterion modified per Amendment 2
 - 2.1 Histologic demonstration of transitional cell carcinoma of the urothelium. Variant urothelial carcinoma histologies such as glandular or squamous differentiation, or evolution to more aggressive phenotypes such as sarcomatoid or micropapillary change are acceptable.
3. Criterion modified per Amendment 2
 - 3.1 Metastatic or locally advanced urothelial cancer (Stage IV disease per AJCC Staging Guidelines)
4. Criterion modified per Amendment 2
 - 4.1 Criterion modified per Amendment 3
 - 4.2 Phase 1b erdafitinib + cetrelimab cohort and **Phase 2:** Meet appropriate molecular eligibility criteria. Tumors must have at least one gene fusion or gene mutation as defined in [Table 4](#).
5. Criterion modified per Amendment 2
 - 5.1 Must have measurable disease by radiological imaging according to the Response Evaluation Criteria in Solid Tumors (RECIST, version 1.1) at baseline.
6. Criterion modified per Amendment 2
 - 6.1 Criterion modified per Amendment 3
 - 6.2 Prior systemic therapy for metastatic urothelial cancer:
 - Phase 1b erdafitinib + cetrelimab cohort:

- Any number of lines of prior therapy
- Renal function for subjects must have a creatinine clearance (CrCl) ≥ 30 mL/min as calculated by Cockcroft-Gault ([Attachment 8](#))
- Phase 1b erdafitinib + cetrelimab + platinum chemotherapy cohort:
 - No prior systemic therapy for metastatic disease. **Note:** Subjects who received neoadjuvant or adjuvant chemotherapy and showed disease progression, within 12 months of the last dose are considered to have received systemic chemotherapy in the metastatic setting
 - Renal function for subjects must have a creatinine clearance (CrCl) ≥ 30 mL/min to receive carboplatin and ≥ 60 mL/min to receive cisplatin as calculated by Cockcroft-Gault ([Attachment 8](#))
- **Phase 2:**
 - No prior systemic therapy for metastatic disease. **Note:** Subjects who received neoadjuvant or adjuvant chemotherapy and showed disease progression, within 12 months of the last dose are considered to have received systemic chemotherapy in the metastatic setting.
 - Cisplatin-ineligible based on:
 - ECOG PS 0-1 AND at least one of the following criteria:
 - Renal function defined as creatinine clearance (CrCl) < 60 mL/min as calculated by Cockcroft-Gault ([Attachment 8](#)) ([Galsky 2011](#))

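### The cisplatin stopping rule in Appendix 2 uses the carboplatin creatinine-clearance limit (30 mL/min) instead of the cisplatin limit (60 mL/min)

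*Protocol*

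**What the plan says.** The creatinine-clearance paragraph of Appendix 2, Section 6.4.4 (below Appendix 2 Table 7) contains three consecutive rules.

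1. Dosing: CrCl must be at least 30 mL/min for carboplatin and at least "60 mL/min to receive cisplatin prior to each cycle of platinum chemotherapy". The same sentence also refers to the Screening value.
2. Delay: "Cisplatin may be delayed for up to 21 days (1 cycle) to allow the subject time to recover from the toxicity".
3. Stopping: cisplatin ends if CrCl has not come back to at least "30 mL/min within 42 days (2 cycles) after the previous dose, cisplatin must be discontinued".

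Elsewhere the cisplatin limit is 60 mL/min:

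- Appendix 2, Section 4.1 (criterion 6.2) requires at least "60 mL/min to receive cisplatin as calculated by Cockcroft-Gault".
- Appendix 3, Section 4.1 includes this among the criteria for cisplatin ineligibility in Phase 2: "Renal function defined as creatinine clearance (CrCl) < 60 mL/min as calculated by Cockcroft-Gault".
- Section 1.7 of the main body draws the line between cisplatin-eligible and cisplatin-ineligible patients at the same value.

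Section 6.4.5 of Appendix 2 warns of cumulative kidney toxicity with cisplatin and adds: "Adequate renal function must be documented prior to receiving the next dose of cisplatin". It gives no value in mL/min.

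**The concern.** The dosing rule and the stopping rule for one drug, in one paragraph, use different CrCl limits, and the stopping limit is the one just given for the other drug. The wording of the stopping rule also assumes that CrCl has fallen below the limit and must climb back to it. A subject held at, say, 50 mL/min was never below 30, so the rule has nothing to act on. Yet 50 mL/min would satisfy the renal criterion for cisplatin ineligibility in this protocol's own Phase 2.

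Two things are at stake. Sites have no instruction for a subject whose CrCl is 30 to below 60 when the delay runs out. And a reader may take recovery to 30 as the condition for resuming cisplatin. This is a safety rule in a dose-escalation cohort, where platinum exposure should be handled the same way at every site because it feeds the dose-limiting-toxicity and dose-selection decisions.

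**Working it through.** This is mainly a consistency check; the arithmetic is short.

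**Inputs**

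- Cisplatin dosing limit: CrCl of at least 60 mL/min, each cycle (Appendix 2, 6.4.4).
- Maximum cisplatin delay: 21 days (6.4.4).
- Mandatory stop: CrCl not back to at least 30 mL/min by 42 days after the previous dose (6.4.4).
- Cycle length: 21 days (two cycles are 42 days; Synopsis and Appendix 2, 3.1.1).
- Planned cisplatin subjects: 3 at 50 mg/m², 6 at 60 mg/m² and about 10 more at the maximum tolerated dose (Section 11.1.1).

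**Timing.** Cycle plus maximum delay = 21 + 21 = 42 days. The protocol's 42-day limit is reproduced, so the time limits agree and only the CrCl limits differ.

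**State of a subject at day 42**

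| CrCl (mL/min) | May be dosed? | May be delayed further? | Must stop under the 42-day rule? |
|---|---|---|---|
| 60 or more | yes | not needed | no |
| 30 to below 60 | no | no | no |
| below 30 | no | no | yes |

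The middle row has no instruction.

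**Does the 60 mL/min limit apply at every cycle?** The first sentence mentions both Screening and each cycle. Appendix 2 Table 1 schedules "Creatinine clearance calculation" on Day 1 of Cycles 1 to 4, and Section 6.4.5 asks for CrCl before each cisplatin dose. Both support the per-cycle reading. If 60 applied only at Screening, 30 would be the only numeric CrCl limit left during cisplatin treatment, which would be worse.

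**Width of the gap.** Fractional loss from an entry value E:

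- re-dosing is barred once the loss exceeds (E − 60)/E;
- the stop rule applies once the loss exceeds (E − 30)/E.

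For E = 60, the lowest admissible value: 0/60 = 0% and 30/60 = 50%. For E = 90, chosen only as an illustration: 30/90 = 33.3% and 60/90 = 66.7%.

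**Number of subjects.** Planned on cisplatin: 3 + 6 + 10 = about 19. The documents give no frequency for the 30-to-below-60 band at day 42. Under an assumed share:

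- 5%: 0.05 × 19 = 0.95
- 10%: 0.10 × 19 = 1.9
- 20%: 0.20 × 19 = 3.8

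That is about 1 to 4 subjects. The shares are assumptions, not protocol figures.

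**After correction.** With 60 in the stopping rule, a subject at day 42 with CrCl of 60 or more is dosed and one below 60 stops. The middle row disappears.

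**The case against.** The strongest reply is that nobody receives cisplatin at 30 to below 60 under this text. The per-cycle limit of 60 bars the dose whatever the stopping sentence says, and other provisions point the same way:

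- Section 6.4.4 requires platinum-related toxicity to settle to Grade 1 or baseline before the next cycle.
- Section 6.4.5 requires adequate renal function before the next cisplatin dose.
- Section 6.4 ties administration to the product label.
- Section 6.4.6 with Appendix 2 Table 8 stops platinum for an unresolved Grade 3 fall in CrCl.
- Section 10.2 obliges discontinuation when the investigator judges it to be in the subject's interest on safety grounds.

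A subject who can be neither dosed nor delayed has in practice finished cisplatin, which is capped at four cycles, and may stay on the other two drugs. Thirty might also have been meant as an absolute floor, separate from the re-dosing limit.

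Much of this stands. Exposure at 30 to below 60 is not authorised, and an individual subject can still be stopped by judgement or by toxicity grade. But none of these provisions sets a CrCl value at which cisplatin must end, so they leave the numerical gap open. The floor reading has no support anywhere in the protocol and does not fit a rule framed as recovery to a limit. It would also leave the middle band without an instruction.

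**Conclusion.** The stopping limit is wrong as written and should be corrected. The 42-day rule should use the cisplatin limit of 60 mL/min; as it stands, a subject at 30 to below 60 is not compelled to stop and has no other permitted course with cisplatin. This rests on the per-cycle reading of the dosing requirement, which the assessment schedule and Section 6.4.5 support; the Screening-only reading does not rescue the rule.

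The practical size is small: only subjects among about 19 planned on cisplatin who are in that band at day 42, or roughly 1 to 4 under the assumed 5% to 20%. The risk is misreading and inconsistent handling between sites, not dosing that the text permits. No Phase 2 estimate, sample size or error rate is touched.

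**What to change.** In Appendix 2, Section 6.4.4, make two text changes.

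- Stopping sentence: *Cisplatin must be discontinued if CrCl is not back to ≥60 mL/min by 42 days (2 cycles) after the last dose.*
- First sentence: *Both at Screening and before every platinum cycle, CrCl must be ≥30 mL/min for carboplatin and ≥60 mL/min for cisplatin.*

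If the sponsor does intend cisplatin to be resumed at 30 to below 60 mL/min, the protocol must say so explicitly and change the per-cycle requirement to match.

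The cost is two sentences and a clarification letter to sites. Design, sample size and assessment schedule do not change.

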6.4.5. Guidance for Specific Platinum Chemotherapy Toxicities

Cisplatin

The toxicity profile for cisplatin is described in the full prescribing information and labeling in the respective current US prescribing information, EU SmPC, or equivalent document for the specific region/country.

For subjects in DL2C, DL2C1 and DL2C2, cisplatin may produce cumulative nephrotoxicity which is potentiated by aminoglycoside antibiotics. Serum creatinine, blood urea nitrogen (BUN), creatinine clearance, magnesium, sodium, potassium, and calcium levels should be measured prior to initiating therapy and prior to each dose of cisplatin. Adequate renal function must be documented prior to receiving the next dose of cisplatin.

Audiometry will be performed for cis-ineligible ONLY if hearing loss is the single reason for cis-ineligibility. Audiometry will be performed as clinically indicated as ototoxicity is cumulative. Hearing loss during the study should be reported as an AE and graded according to CTCAE version 5.0.

Carboplatin

The toxicity profile for carboplatin is described in the full prescribing information and labeling in the respective current US prescribing information, EU SmPC, or equivalent document for the specific region/country.

For subjects in DL2D and DL2D1, bone marrow suppression (leukopenia, neutropenia, and thrombocytopenia) is dose-dependent and is also a DLT. Peripheral blood counts should be monitored frequently and, when appropriate, until recovery is achieved. Carboplatin can induce emesis, which can be more severe in patients previously receiving emetogenic therapy.

